**STUDY PROTOCOL AND STATISTICAL ANALYSIS PLAN**

## 1. Methods

### 1.1. Study design

This will be a multisite randomized active-comparator controlled clinical trial. Due to the nature of the intervention, subjects and investigators will not be able to be masked to the intervention. The assessor will not be able to be masked to group assignments, as the presence or absence of certain variables in the dataset, namely the perturbation level, will immediately reveal group assignment.

**Sample Size Estimation and Study Timeline:** Using the pilot data, a Cohen's d effect size of 0.39 was calculated and a two-tailed power analysis ( $\alpha=0.05$ ) was conducted. For the observed effect size, an estimated sample size of 214 participants would achieve 80% power. Using this estimate, and the estimates of the participating sites of the number of potential subjects that could be recruited, enrollment is expected to last 12-18 months (Table 1).

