**Table 1. General Timeline**

Year 1	Month											
	1	2	3	4	5	6	7	8	9	10	11	12
Clinical Trial Registration 	X											
Purchasing 	X											
Staff Training/Check-in	X			X					X			
Steering Committee meeting	X	X	X	X	X	X	X	X		X	X	X
Enrollment Target 		12	12	12	12	12	12	12	12	12	12	12
Completion Target 			12	12	12	12	12	12	12	12	12	12
Interim data analysis (25% and 50% recruitment)							X				X	
Year 2	Month											
	13	14	15	16	17	18	19	20	21	22	23	24
Staff Training/Check-in	X											
Steering Committee meeting	X	X	X	X	X	X	X	X	X	X	X	X
Enrollment Target 	12	12	12	12	12	12	12					
Completion Target 	12	12	12	12	12	12	12	12				
Data analysis									X	X		
Manuscript preparation; Poster abstract submission										X	X	X
Clinical Trial Registration: Data updates 										X	X	

This study will be registered and maintained at clinicaltrials.gov; Registration will be completed prior to recruiting the first subject.

If grant funding is able to be attained, purchasing outlined in the grant will be completed in month 1 of the award period.

Enrollment and completion targets are estimates based on an 18 month enrollment period. For a 12 month enrollment period, the enrollment and completion targets would be 18 participants per month, with the completion target ending in month 13.

**Participants, Settings, and Inclusion/Exclusion Criteria:** To participate in this study, participants must be recruited at one of the three participating rehabilitation centers: Gaylord Specialty Healthcare (Wallingford, CT), MedStar National Rehabilitation Hospital (Washington, DC), or Spaulding Rehabilitation Hospital Cape Cod (Sandwich, MA).

To be eligible for study participation, subjects must meet the following *Inclusion Criteria*:

- Admitted to one of the listed study locations for inpatient rehabilitation following either

ischemic or hemorrhagic stroke and medically stable for the therapy program.

- Be 18 years of age or older.
- Discharge date of 10 days or longer at study consent
- Have at least a moderate fall risk or better, shown by an admission BBS score of 21/56 or greater.
  - Patients that score below 21 or are non-ambulatory will not be considered for this study.

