Descriptive data is reported as mean (95% confidence interval). If hypothesis testing was done, data were reported with a p-value, and significance was set at  $\alpha=.05$ . The primary outcome measures used in our analyses were the BBS, ABC, 10MWT, CMS GG0130 Mobility scores, and CMS GG0170 Self-care scores. Data were determined to be missing completely at random and were dealt with via complete case analysis and mixed-effects analysis as applicable. Data were also assessed for violations in assumptions of their given tests, and were dealt with via non-parametric analysis as necessary.

Categorical data was analyzed using Chi-square testing. Unpaired t-tests or Mann-Whitney U tests were utilized as necessary to evaluate between-group differences in continuous outcome variables.

Analysis of covariance (ANCOVA) was used to account for between group differences while controlling for covariates. To evaluate if there were differences between pre- and post-intervention data, a 2-way analysis of variance (ANOVA) was utilized, with mixed-effects analysis being utilized when data was missing. Differences in average improvement by number of sessions completed were evaluated using a 2-way ANOVA. Differences in outcome measure between testing sites were analyzed using one-way ANOVA or Kruskal-Wallis testing. Multiple comparisons were analyzed using, Fisher's, Dunn's, Tukey's multiple comparison tests as appropriate.

References:

2. Parametric ANCOVA and the Rank Transform ANCOVA When the Data are Conditionally Non-Normal and Heteroscedastic - Stephen F. Olejnik, James Algina, 1984 [Internet]. [cited 2024 Apr 4]. Available from: <https://journals.sagepub.com/doi/10.3102/10769986009002129>

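### Five outcomes are declared primary at .05 with no success rule and no adjustment across them; if any one significant result counts, the false-positive chance is about 10–23%, not 5%

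*Combined protocol and SAP*

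**What the plan says.** All of the relevant text is in section 1.1.

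- **Primary outcomes (Data Analysis).** "The primary outcome measures used in our analyses were the BBS, ABC, 10MWT, CMS GG0130 Mobility scores, and CMS GG0170 Self-care scores".
- **Significance level (Data Analysis).** Where hypotheses were tested, "data were reported with a p-value, and significance was set at" .05. The level is not divided among outcomes.
- **Between-group tests (Data Analysis).** "Unpaired t-tests or Mann-Whitney U tests were utilized as necessary to evaluate between-group differences in continuous outcome variables", and "Analysis of covariance (ANCOVA) was used to account for between group differences while controlling for covariates". The text does not say which of these is the primary test for a given outcome. It does say that assumptions were checked and that non-parametric methods were used where needed.
- **Multiple comparisons (Data Analysis).** "Multiple comparisons were analyzed using, Fisher's, Dunn's, Tukey's multiple comparison tests as appropriate". This sentence closes a paragraph on ANOVA and Kruskal-Wallis analyses by time, number of sessions and site.
- **Sample size.** "Using the pilot data, a Cohen's d effect size of 0.39 was calculated", and "For the observed effect size, an estimated sample size of 214 participants would achieve 80% power". The calculation is two-tailed at 0.05, and the outcome is not named.
- **Interim looks.** Table 1 schedules interim analyses at 25% and 50% of recruitment. The recruitment paragraph lets screening end when statistical guidelines fixed in advance are met, but does not give them.
- **Outcome collection.** BBS, ABC and 10MWT are set prospectively under Equipment and Instruments and in Table 2. The two GG scores are named in neither place, though Table 2's row for demographic and other secondary information could cover them.

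**The concern.** Five primary outcomes are legitimate if the plan says how they combine into a conclusion. This plan does not. Two readings are open, and they have opposite consequences.

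On the first, any significant outcome supports a positive primary result. Each of the five tests then carries its own 5% risk, and the risk for the trial's main claim is larger. On the second, all five must be significant. The main claim is then protected, but the trial is much less likely to succeed than the stated 80% suggests.

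A reader of the results cannot tell which rule applies, or which of the five outcomes the trial was sized for. The trial's principal conclusion depends on both.

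**Working it through.** **Inputs.** From the documents: 5 primary outcomes and significance at .05 (Data Analysis); two-tailed testing, d = 0.39 and 214 participants (sample-size paragraph); equal allocation (Subject assignment), hence 107 per arm. Not in the documents: the correlation among the five outcomes. I assume one common pairwise value ρ and vary it from 0 to 0.9. All five scores come from the same patients, so ρ = 0 is a limiting case.

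**Step 1: reproduce the plan's figure.** Per arm, n = 2(1.960 + 0.842)² / 0.39² = 103.2, so 104 per arm and 208 in total. The t-test version gives 104.2, so 105 per arm and 210 in total. With 107 per arm, t-test power is 81.0%. The stated 214 is therefore consistent with one outcome, tested once at an unadjusted .05.

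**Step 2: false-positive chance if any one outcome counts.** One test per outcome, one final look, no true effect.

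- Independent outcomes: 1 − 0.95⁵ = 0.2262.
- Correlated outcomes: 1 − ∫ φ(u) [Φ((1.96 − √ρ·u)/√(1−ρ)) − Φ((−1.96 − √ρ·u)/√(1−ρ))]⁵ du.

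**Step 3: power if all five must be significant at .05, each with d = 0.39.** The mean of each test statistic is 0.39 × √(107/2) = 2.853. Single-outcome power (normal approximation) is Φ(2.853 − 1.960) = 0.814.

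- Independent outcomes: 0.814⁵ = 0.357.
- Correlated outcomes: ∫ φ(u) Φ((0.893 + √ρ·u)/√(1−ρ))⁵ du.

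| ρ (assumed) | Any-one false positive | All-five power |
|---|---|---|
| 0 | 22.6% | 36% |
| 0.3 | 20.9% | 47% |
| 0.5 | 18.3% | 54% |
| 0.7 | 14.8% | 61% |
| 0.8 | 12.7% | 65% |
| 0.9 | 10.2% | 71% |

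**Step 4: effect of Holm's method.** With no true effect, a false claim needs the smallest of the five p-values to fall below .05/5 = .01. At ρ = 0 this has probability 1 − 0.99⁵ = 4.9%. By the integral in step 2 with the .01 critical value, it is 4.2% at ρ = 0.5 and 2.3% at ρ = 0.9.

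Power for one outcome by unadjusted t-test, 107 per arm, d = 0.39, is 81% at .05 and 60% at .01. The 60% is a floor, because Holm relaxes the threshold after each rejection. If all five outcomes have d = 0.39, simulated power for a given outcome is 73% at ρ = 0 and 68% at ρ = 0.9.

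**Step 5: why these power figures do not carry over to ANCOVA.** Adjusting for the pre-intervention value removes part of the variance. The documents give no pre-post correlation. If it were 0.5, the effective d would be 0.39/√(1 − 0.5²) = 0.45, and power would be about 91% at .05 and 76% at .01.

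**The case against.** **The plan names multiple-comparison procedures.** It does, but Fisher's, Dunn's and Tukey's tests compare groups or factor levels within one outcome. None of them combines evidence across BBS, ABC, 10MWT and the GG scores.

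**The success rule may exist elsewhere.** This stands in part. The text points to descriptions that the public document does not contain, so the absence can be asserted only of the public document. The statistical guidelines in the recruitment paragraph appear only as a reason to end screening, so they cannot be read as a success rule.

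**The five may be co-primary.** Possible, and then error is not inflated. The plan does not say so, and the 80% would not then describe the chance of success.

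**The correlations are assumed.** True. But over the whole range examined, the any-one error is at least twice the stated level.

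**Holm is one choice among several.** This stands. A documented single primary outcome would serve as well.

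Three stronger readings are tempting, and the documents do not support them.

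- A reader might infer that the most favourable of the t-test, Mann-Whitney U and ANCOVA could be reported for each outcome. The text ties non-parametric analysis to assumption checks, and the ANCOVA references concern the rank-transformed version. How ANCOVA relates to the unadjusted tests is unclear, but nothing licenses choosing by p-value.
- A reader might infer that the GG scores were promoted to primary after the results were known. They are named only in past-tense text, which raises the question of timing but does not answer it.
- A reader might infer that the interim looks inflate error further. The documents do not say whether these outcomes were tested at the interims.

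**Conclusion.** The concern holds. As written, the plan allows a positive primary claim on any one of five outcomes, each tested at .05. On that rule the false-positive chance is 22.6% at ρ = 0, 18.3% at 0.5 and 10.2% at 0.9, about two to four and a half times the stated level. This rests on assumed equal correlations, one test per outcome and one final look. It is conditional on the any-one rule: the plan leaves that rule open but does not adopt it, so 10–23% is not an established error rate for the trial.

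Under an all-five rule the problem is power: 36–71%, assuming unadjusted tests and d = 0.39 for every outcome. Either way the 80% describes a single unnamed outcome, not the success of the trial. The sample size of 214 reproduces and is not in dispute.

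It would also be too strong to say that power under Holm is 60%. That is the floor for an unadjusted t-test; it is higher if several outcomes respond or if ANCOVA is the primary test.

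**What to change.** **Data Analysis.**

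- State that the between-group tests of the five primary outcomes are adjusted by Holm's method at a family-wise two-sided .05, and that all other analyses are supportive. Holm is valid whatever the correlations.
- Name one test per outcome. An example is ANCOVA of the post-intervention value on the pre-intervention value, with the rank version already cited as the fallback under the existing assumption check.
- Acceptable alternative: one primary outcome, supported by a record dated before data review, with the other four secondary.
- If either choice was made after results were seen, label it post hoc and check it against the trial registration promised in Table 1, footnote 1.
- State which pre- and post-intervention values define the two GG scores, and when they were made primary.

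**Sample size.** Name the outcome behind d = 0.39, and state that the 80% applies to that outcome alone at an unadjusted .05. Any restated power must match the chosen test and show its assumptions.

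**Interim analyses.** Say whether the primary outcomes were tested at 25% and 50% of recruitment. Reconcile this, and the guidelines for ending screening, with the success rule.

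**Cost.** No more patients or data are needed. Before analysis, the change is wording and a p-value adjustment. If the analysis is complete, p-values must be readjusted and some conclusions may need restating. The downside is lower power for each single outcome or, under the alternative, four outcomes lose primary status.

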**Subject identification, recruitment, and pre-assessments:** As described above, qualifying patients will initially be screened/identified through internal reports generated at each study site summarizing admission BBS scores for recently admitted patients. Screening will continue until the target number of participants have completed the study and/or the pre-determined statistical guidelines have been met. After initial screening, the additional inclusion/exclusion criteria will be considered with attending physician approval and the patient approached for consent. After collecting informed consent, participants will be asked to complete an ABC scale pre-assessment. If it was not already conducted by the participant's primary physical therapist at admission, a 10MWT pre-assessment will be conducted within the 48 hours prior to the first treatment session. The admission BBS score will be counted as the participants' BBS pre-assessment. Study procedures and assessments will be conducted according to the general timeline shown in **Table 2**.

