**BWSS Standard Intervention Control Group:** The BWSS control group will conduct at least 2 and up to 6 study related therapy sessions. Study related therapy sessions will last a minimum of 15 minutes up to 30 minutes. Study sessions will be completed over a 2 to 3 week period as part of the subject's inpatient therapy program. Each session must have an active time of at least 15 minutes in the system to be included, up to 30 minutes for each session. To be as pragmatic and clinically relevant as possible, treatment sessions will be incorporated directly into the participants' normal care. Furthermore, we are allowing participants to complete 2 to 6 sessions as dictated by short or unexpected changes to the discharge planning timeline. During each session, participants will conduct balance exercises, including: marching, side-stepping, retro-ambulation, step-taps, and step-ups. They will also conduct various standard gait exercises, including: ambulation over the ground, going up and down stairs, and performing sit-to-stand transitions. Each of the 2 to 6 study sessions will be part of the subject's normal course of therapy. As this is an active clinical comparison, clinical parameters and progression, other than those described

above, will be determined by the treating therapist (i.e. percent body weight support and use of assistive devices) to ensure success and appropriate challenge to the subject.

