**BWSS-P Intervention Group:** The BWSS-P intervention group will also conduct 2 to 6 study sessions over a two-week period. Each session must have an active time of at least 15 minutes in the system, up to 30 minutes for each session. Participants in the BWSS-P group will conduct the same balance and gait exercises as the control group, however, these sessions will include eight perturbations, two in each direction (lateral left, lateral right, anterior, and posterior). Perturbations will occur while static/standing (lateral, anterior, posterior) and dynamically while ambulating (anterior, posterior). Each of the 2 to 6 study sessions will be part of the subject's normal course of therapy. As this is an active clinical comparison, clinical parameters and progression, other than those described above, will be determined by the treating therapist (i.e. percent body weight support and use of assistive devices) to ensure success and appropriate challenge to the subject. The TRiP or perturbation level will be progressed to the point of loss of balance, or very near loss, without recovery. The perturbation level should then be then decreased by one level for treatment. All 8 perturbations will occur at this level until it is clinically appropriate to progress again. The intensity of TRiP perturbation ranges from level 1 to 10, minimal to maximum, respectively.

**Post-Assessments:** After the completion of the subjects' final BWSS session before discharge, investigators will conduct an ABC and 10MWT post-assessment no longer than 48 hours following the final session. Follow-up BBS are often completed prior to discharge as part of patient/participant's standard of care. However, in the case that there is an unexpected delay or there is a significant length of time until the participant's discharge, a post-assessment BBS will be conducted no longer than 48 hours following the last session.

**Data Analysis:** Data were analyzed using GraphPad Prism (version 10; GraphPad Software, Boston, MA) and RStudio (version 4.2.2, Posit Software, PBC, Boston, MA] using the *car* package.

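### Improvement is tested by number of sessions completed, a non-randomised count set largely by discharge timing, so any session effect found cannot be separated from elapsed recovery and patient selection

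*Combined protocol and SAP*

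**What the plan says.** The Data Analysis section plans this comparison in one sentence: "Differences in average improvement by number of sessions completed were evaluated using a 2-way ANOVA". It does not name the second factor, the outcome or any covariate. The same section attaches p-values at the 0.05 level to hypothesis tests. It mentions ANCOVA separately, without listing covariates or linking it to the session analysis. Nothing labels the session analysis exploratory.

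The paragraph on the BWSS control group explains what sets the count: "we are allowing participants to complete 2 to 6 sessions as dictated by short or unexpected changes to the discharge planning timeline". A second rule also affects it: "Each session must have an active time of at least 15 minutes in the system to be included".

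The start of the BBS interval is given under subject identification and pre-assessments: "The admission BBS score will be counted as the participants' BBS pre-assessment". Its end is given under Post-Assessments. It is either a usual-care BBS before discharge or, when discharge is delayed or distant, "a post-assessment BBS will be conducted no longer than 48 hours following the last session".

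The treatment windows differ by arm. For control: "Study sessions will be completed over a 2 to 3 week period as part of the subject's inpatient therapy program". For BWSS-P: "The BWSS-P intervention group will also conduct 2 to 6 study sessions over a two-week period".

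**The concern.** Participants who complete six sessions differ from those who complete two in more than sessions. They may have spent longer in inpatient rehabilitation between the two BBS scores, with more spontaneous recovery and more usual therapy. They may also be the slower or more severely affected patients, since stays depend on progress. A two-way ANOVA with sessions completed as a factor attributes all of this to the session count.

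If the unnamed second factor is arm, any arm contrast within a session count compares groups formed after randomisation, so the protection of randomisation is lost within those cells.

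At stake is what the trial may say about the number of sessions. A significant result would invite the conclusion that more sessions produce more improvement, and a null result the opposite. The design supports neither.

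**Working it through.** **1. The plan's own figure.** The inputs under Sample Size Estimation are d = 0.39, two-sided alpha 0.05 and 80% power. The normal approximation gives n per arm = 2 × (1.960 + 0.842)² / 0.39² = 103.2, so 104 per arm and 208 in total. The two-sample t-test gives 105 per arm, 210 in total. At 107 per arm the power is about 81%. The stated 214 is sound, and this point does not touch it.

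**2. What the passages imply.** The count is fixed by events after assignment (control-group paragraph). The BBS interval starts at admission and ends at a point tied to the last session or to discharge. The length of exposure to recovery can therefore vary with the count, and the plan does not adjust for it.

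**3. Size with no true session effect.** Assumptions not in the documents: counts 2 to 6 equally likely, residual SD 1, recovery r of 0.02 to 0.05 SD per day, and a mean interval rising linearly with the count. If the interval is D days longer at six sessions than at two, the spurious gap is G = r × D. Five equally spaced means with range G have variance G²/8, so the noncentrality is λ = 214 × G²/8. The sessions term of a two-way ANOVA with arm has 4 and 204 degrees of freedom (214 − 10 cells).

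| Interval, 2 to 6 sessions | r | G (SD) | λ | Rejection |
|---|---|---|---|---|
| 10 to 14 days | 0.02 | 0.08 | 0.17 | 5.8% |
| 10 to 14 days | 0.05 | 0.20 | 1.07 | 10.8% |
| 14 to 21 days | 0.02 | 0.14 | 0.52 | 7.7% |
| 14 to 21 days | 0.05 | 0.35 | 3.28 | 25.9% |

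Simulation of these settings gave about 7% to 27%, which agrees within simulation error.

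**4. Interval proportional to sessions.** At three sessions a week (4.7 to 14 days), G is 0.19 to 0.47 and rejection is about 10% to 45%. At two a week (7 to 21 days), G is 0.28 to 0.70 and rejection is about 18% to 83%.

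**5. Direction.** Let the two-session group recover k times as fast as the six-session group, over 10 and 14 days respectively. Then G = r × (14 − 10k). For k = 1.5 this is −0.02 to −0.05 SD. For k = 2 it is −0.12 to −0.30 SD. The apparent effect reverses.

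**6. Effect of adjustment.** In simulations with interval = 4 + 2 × sessions days, SD 3, and r of 0, 0.02, 0.05 and 0.10, the unadjusted sessions term rejected in 4.5%, 8.2%, 32% and 89% of trials. With the interval as a covariate, rejection was 4.6% to 5.5%. The arm-by-sessions interaction stayed at 4.7% to 6.0% when recovery and session pattern were the same in both arms.

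**The case against.** Several objections stand. The analysis is additional to the randomised comparison. The plan speaks only of differences in average improvement and never claims a dose-response, so the risk lies in the reading it invites. Discharge timing is the stated driver of the count but not the only one, because the active-time rule and tolerance also matter. BBS improvement starts at admission, and patients may enrol later once they reach the threshold score, so a long interval can go with few sessions. The size depends on recovery rates and intervals that the documents do not give.

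A reader might infer three stronger things that the documents do not support:

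- **A false-positive rate above 80%.** That needs six sessions to take 21 days, which exceeds the two-week window stated for BWSS-P.
- **A spurious arm-by-sessions interaction.** No calculation shows one. The interaction stays near 5% when the arms share the same recovery and session pattern. The differing windows could break that symmetry, but by how much is unknown.
- **A bias that always favours more sessions.** Step 5 of the working shows that it can go the other way.

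It might also be suggested to replace sessions completed with planned days to discharge, since eligibility requires "Discharge date of 10 days or longer at study consent". That variable is fixed before assignment, but it answers a different question. The plan gives only a threshold, and Table 2 does not list planned days as an item to record.

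None of this removes the core point: the factor is non-randomised, the interval is not fixed, and the test carries no adjustment.

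**Conclusion.** The concern holds as a limit on one additional analysis. As written, the test cannot distinguish an effect of sessions from elapsed recovery, usual therapy or selection into session count, and the bias may run in either direction. Under the intervals in step 3, a null session effect is rejected in roughly one trial in 17 to one in 4, against a nominal one in 20. At the lower end the inflation is negligible. These figures rest on assumed recovery rates, intervals and session distribution, and on equal recovery rates across counts, so they illustrate the problem rather than predict its size. A reader might extend the point to the main between-arm result, but the documents do not support that: the arms are compared as randomised, and the 214 reproduces.

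**What to change.** Amend the Data Analysis section as follows:

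- Describe improvement by sessions completed as exploratory and non-causal. Present it as means with 95% confidence intervals and make no dose-response claim.
- Name the outcome and both factors.
- If a test is kept, fit a model for improvement with sessions completed, arm, baseline score and pre-to-post interval in days. State that this addresses elapsed time only to the extent that the interval varies within a session count, and that it does not remove selection into that count.
- State that arm contrasts within session-count strata will not support efficacy conclusions.
- Reconcile the two descriptions of the treatment window, because unequal windows would make the relation of sessions to elapsed time differ by arm.

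The cost is small: SAP wording, an interval derived from assessment dates, and the loss of an unadjusted p-value. The section is written in the past tense, so if the analysis has already been run, the same wording belongs in the report.

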**Table 2. Schedule of Study Procedures and Assessments**

Procedure	Admission	Screening	Pre- Intervention	Treatment Sessions						Post- Intervention
				1	2	3	4	5	6	
BBS	X									X
Report generation	X									
Informed consent		X								
Participant group assignment			X							
Collection of demographic and other secondary information as described below 				X						X
Additional stroke information 				X						X
ABC scale				X						X
10MWT				X						X
BWSS Control Intervention					X	X	X	X	X	X
BWSS-P Intervention					X	X	X	X	X	X
TRiP/Perturbation level recording					X	X	X	X	X	X
System on-time/off-time recording					X	X	X	X	X	X
Data transfer										X

The described information can be collected, as available, any time after the subject has consented to the study, but before de-identified data is transferred to the Lead Site.

**Subject assignment:** Consented subjects will be assigned to either the BWSS Standard Intervention (Control) Group or BWSS with Balance Perturbations (BWSS-P) Intervention Group according to a pre-generated randomized assignment sheet. Each randomized assignment sheet will consist of equal BWSS Control and equal BWSS-P assignments whose order has been randomized using the random list generator at <https://www.random.org/lists/>. Co-Investigators at each site, who will not be delivering the study interventions directly, will be given a unique list with a number of assignments that is in proportion to the number of subjects expected to be recruited at the site; additional assignment lists will be generated if needed. These co-Investigators will be responsible for communicating group assignments to study therapists delivering the intervention, and for ensuring that randomization and treatment order is maintained. It is expected that if the assignment scheme is not maintained for whatever reason, that they will report the incident to the steering committee, described below, and how it was/or still needs to be rectified. No matter group assignment, all consented subjects will be asked to conduct all pre- and post-assessments.

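### Fisher's test is listed for multiple comparisons without restriction; applied to the five session counts it would not hold the family error at 5%

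*Combined protocol and SAP*

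**What the plan says.** All analysis text is in the Data Analysis section of the combined protocol and SAP.

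- Error level: "data were reported with a p-value, and significance was set at" .05. No family is defined over which that level is held.
- Session count: "Differences in average improvement by number of sessions completed were evaluated using a 2-way ANOVA". One factor is the number of sessions; the other is not named.
- Sites: "Differences in outcome measure between testing sites were analyzed using one-way ANOVA or Kruskal-Wallis testing".
- Follow-up tests: "Multiple comparisons were analyzed using, Fisher's, Dunn's, Tukey's multiple comparison tests as appropriate". No test is matched to an analysis, and no overall test is made a condition for Fisher's.

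The number of groups comes from elsewhere in the document. The description of the control group says "we are allowing participants to complete 2 to 6 sessions as dictated by short or unexpected changes to the discharge planning timeline", and the BWSS-P description gives the same range, so there are five session counts. Under Subject assignment, participants are "assigned to either the BWSS Standard Intervention (Control) Group or BWSS with Balance Perturbations (BWSS-P) Intervention Group", so there are two arms. Under the eligibility heading, "participants must be recruited at one of the three participating rehabilitation centers", so there are three sites.

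**The concern.** In a list of multiple-comparison tests, Fisher's is naturally read as the least significant difference (LSD) procedure. That procedure tests every pair at the unadjusted 0.05 level. Requiring a significant overall F test first protects the family when all means are equal. When some means differ and others do not, that protection is complete only for three groups. With more groups, one real difference opens the gate, and the remaining true nulls are then tested with no correction.

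Tukey's and Dunn's tests are meant to correct for the number of pairs; Fisher's is not. A list that offers all three without assigning them lets an uncorrected result be reported as a multiple-comparison result. What is at stake is the reliability of pairwise statements about how improvement varies with the number of sessions.

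**Working it through.** **The plan's own figure.** The Data Analysis section states no family-wise error rate. The only related figure is the sample size, based on an "effect size of 0.39 was calculated and a two-tailed power analysis" at α = 0.05 with 80% power, giving 214. The normal approximation gives n per arm = 2(1.960 + 0.842)²/0.39² = 103.2, so 104, or 208 in total. The t-test calculation gives 104.2, so 105, or 210 in total. An unrounded d of about 0.385 gives exactly 214. The figure is reproduced to within rounding of d, and N = 214 is used below.

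**Inputs.** N = 214; 0.05 per pair; k = 5 session counts, hence 5 × 4/2 = 10 pairs; 3 sites, hence 3 pairs; 2 × 5 = 10 arm-by-session cells if arm is the second factor, hence 10 × 9/2 = 45 pairs. Near-equal group sizes are an assumption, because the plan gives no expected distribution of session counts.

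**Method.** With equal groups and all means equal, some pair exceeds the unadjusted limit when the studentized range exceeds q = √2 × t(0.975, N − k). The ungated family error is therefore P(Q(k, N − k) > q). If one group differs by enough that the F test is virtually certain to be significant, the error among the others is P(Q(k − 1, N − k) > q).

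**Session counts (k = 5, df = 209).** t = 1.971, so q = 1.414 × 1.971 = 2.788.

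- No F test required: 28.4%.
- F test required, all counts equal: 5.0% (simulation).
- F test required, one count truly different (6 true nulls): 20.2%.
- Tukey, all counts equal: 5.0%.

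A simulation with 200,000 runs gave 28.4% and 20.4% for the first and third cases. With group sizes of 20, 30, 40, 50 and 74 it gave 27.7% and 20.0%, so the equal-size assumption matters little.

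**Sites (k = 3, df = 211).** Ungated: 12.2%. With the F test required: 5.0% whether all three means are equal or one differs.

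**Arm within each session count (5 contrasts), if arm is the second factor.** As the contrasts are close to independent, 1 − 0.95⁵ = 22.6%; simulation gave 22.4% ungated. With the F test on all ten cells required, it was 3.8% if all cells are equal, and 22.4% if session counts differ strongly but arms do not. Bonferroni at 0.05/5 = 0.01 each gave 4.8%.

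**All 45 pairs of ten cells (df = 204), worst case.** Ungated 62.0%; with one cell truly different and the F test passed, 56.5%. Tukey gave 4.9% in simulation with all cells equal.

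**Price of Tukey.** For five groups the critical value is 2.75 against 1.97 unadjusted: 2.75/1.97 = 1.40, so intervals about 40% wider.

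All rates are per outcome. The plan names five primary outcomes, and each could carry its own set of comparisons.

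**The case against.** The strongest reply is that the plan never ties Fisher's to session counts. The qualifier at the end of the sentence could confine it to the three sites, where F-protected LSD is valid, or to the few contrasts in the pre/post analysis. Tukey's and Dunn's are listed as well, so controlling methods are available. This stands in part. The documents do not show that an uncontrolled test will be used for session counts, but nothing in them prevents it either.

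Two stronger readings are tempting. A reader might infer a false-positive chance near 60%. That needs arm to be the unnamed second factor and all 45 pairs of cells to be tested, including contrasts such as control with two sessions against BWSS-P with six. The plan states neither. A reader might also infer that site comparisons are badly inflated. They are not if the overall test comes first; 12% arises only if it is ignored, and the plan is silent on that.

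It is also fair to say that little depends on this. The number of sessions follows discharge timing and is not randomised, so these comparisons cannot carry a causal claim even with perfect error control.

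**Conclusion.** The point holds as a flaw in specification. Fisher's is an allowed test with no restriction, and it fails for any family of more than three groups. If it is applied to the session counts, the chance of at least one false pairwise difference per outcome is about 28% without an F test first, and about 20% with one when a single count truly differs, against 5% with Tukey. These figures assume N = 214 and near-equal groups, and change little under the unequal split tried. The ten-cell figures of about 62% and 56% are a worst case only.

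A reader might take this as a threat to the trial's main result. The documents do not support that: the between-arm comparison has two groups and needs no pairwise procedure, and the sample size does not depend on it. This is a cheap improvement to secondary comparisons.

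**What to change.** Replace the sentence on multiple comparisons with an assignment of test to analysis:

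- Name the second factor of the session-count ANOVA and the family over which error is held.
- Use Tukey for session-count pairs after the parametric model.
- Use Holm or Bonferroni for any arm-within-session contrasts. All-pairs Tukey over ten cells would be needlessly conservative for five contrasts (critical value 3.20, against 2.60 for Bonferroni).
- Use Dunn with adjusted p-values after Kruskal-Wallis.
- Do not use Fisher's for any family of more than three groups. It may stay for the three-site comparison, only after a significant F test.
- Report adjusted p-values and intervals.

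The section is written in the past tense. If the analyses have already been run, the report should say which test produced each pairwise result and give the adjusted values.

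The cost is a few lines of SAP text and some precision: session-count intervals become about 40% wider than with Fisher's. No change to recruitment or to the main between-arm analysis is needed.
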